## 1. Introduction

This document presents the statistical analysis plan (SAP) for BNT162-01, a dose-escalation phase I/II study in healthy and immunocompromised subjects. The results of this study might be included in a regulatory submission.

This SAP describes the detailed procedures for the planned statistical analyses for protocol version 13.0, dated 12 January 2022 (hereinafter referred to as "the protocol"). Changes from the protocol are documented in Section 7.1 Appendix 1.

The study consists of two parts, Part A and B. All analyses of Part A except for exploratory endpoints are described in this SAP including the analysis of CRF and laboratory data. The exploratory endpoint analyses will be described in a separate biomarker SAP developed by BioNTech. Due to changes in the overall clinical development plan, Part B will no longer be conducted.

The statistical analyses described in this document will be conducted by Staburo GmbH using SAS® software version 9.4 or higher.

This study will evaluate safety, adverse events and immunogenicity assessments data.

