## 6. Statistical Analyses

## 6.1. General Considerations

The following described statistical analyses only refer to Part A of the study.

No formal statistical testing will be done.

Unless otherwise specified, analyses will be based on data pooled across all study sites.

Data assessed after the vaccination with a non-trial vaccine will be excluded from all statistical analyses.

Clarifications:

- Data assessed on the same day as the non-trial vaccination will remain in the analysis.
- If the date of non-trial vaccination is missing, but month and year information is available, data assessed after the last day of the respective month will be excluded from statistical analysis.

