## 6.1.1. Tables and Listings

#### Tables

In general, data will be summarized by groups (i.e., by vaccine type [BNT162a1, BNT162b1, BNT162b2, BNT162c2 SD and BNT162c2 P/B] and cohort) and all cohorts combined for each type (cohort-total). Furthermore, selected cohorts may be combined. The cohorts and cohort-total will be presented in columns and the different vaccine types in different tables.

There may be additional total columns for younger (18 to 55 years) and older (56 to 85 years) subjects.

Descriptive summary tables as well as figures will be based on scheduled visits.

Continuous variables will be summarized by group using the following descriptive statistics: number of subjects with non-missing data (n), mean, standard deviation (SD), median, minimum (min) and maximum (max).

Descriptive statistics of titer and fold increase of titer will additionally include geometric mean and its two-sided 95% confidence interval (CI). The geometric mean titer (GMT) is calculated as the mean of the logarithm of the functional antibody titers, back-transformed into the original scale. Two-sided CIs will be obtained by calculating CIs using t-distribution for the mean of the logarithmically transformed assay results and transforming the limits back to the original scale.

Geometric mean fold rise (GMFR) is calculated as the mean of the difference of logarithmically transformed assay results (post vaccination time point – pre vaccination time point) and back-transformed into the original scale. Two-sided CIs will be obtained by calculating CIs using Student's t-distribution for the mean difference of the logarithmically transformed assay results and transforming the limits back to the original scale.

Categorical variables will be summarized by group presenting absolute and relative frequencies (n and %) of subjects in each category (including the category 'missing' if applicable).

Percentages will be calculated based on the number of subjects in the respective analysis set (N) as denominator if not stated differently. Percentages may be presented with exact 95% Clopper-Pearson CIs.

SDs as well as CIs will only be calculated if values of at least 3 subjects are available.

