#### **Analysis Sets**

The SCR will be used for disposition. The SAF will be used for analysis of safety and adverse events data. Some analyses of the adverse events will be repeated using the SAFB if the SAF and the SAFB sets differ. The IMM will be used for the analysis of immunogenicity data. The analyses of all vaccines may be repeated using the IMMPP if the two analysis sets differ significantly. This will be decided at the data review meeting.

If subjects by accident receive two different doses or vaccines, they will switch the group and will be displayed for each immunization with the corresponding group. For combined analyses, subjects who received two different doses will be assigned to the lower dose. Subjects who receive different doses as per protocol will be presented in their respective group.

Data of subjects who failed to complete all visits of the study (dropout or withdrawal) will be reported as far as their data is available.

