#### 6.4.3. Adverse Events

#### Definition

For detailed information on adverse events see section 10.3 of the protocol.

Adverse events (AEs) will be coded using the Updated Version MedDRA® 23.0 including specific terms for COVID-19 to get a system organ class (SOC) and preferred term (PT) for each AE.

A treatment emergent adverse event (TEAE) is defined as any AE with an onset after the first immunization (if the AE was absent before the first immunization) or worsened after the first immunization (if the AE was present before the first immunization). AEs with an onset date more than 28 days after the last immunization will be considered as treatment emergent only if assessed as related to IMP by the investigator. AEs that cannot be determined to not be treatment emergent due to missing date or time will be defined as TEAE.

Clarification: To clarify the definition in the protocol, AEs with an onset date at the date of the first immunization will only be considered as treatment emergent if the AE occurred after the first immunization.

The TEAEs will be evaluated for the following time intervals, clarifying and harmonizing the intervals defined in the protocol:

- Prime immunization up to boost immunization or day 28 (inclusive) after initial immunization (whatever comes first)
- Boost immunization up to day 28 (inclusive) after boost immunization
- All TEAEs (regardless of relationship assessment) occurring from

- Prime immunization up to day 28 after boost immunization (inclusive).
- If no boost immunization, up to 28 days (inclusive) after prime immunization
- All TEAEs assessed as related through visit 10.

The intervals starting or ending with an immunization, will start or end with the date and time of the immunization. TEAEs are assigned to the time intervals according to their start date and time. AEs with missing date will be assigned to each of the respective intervals if it cannot be ruled out, that it belongs to the time interval.

Deviating from the protocol, the time intervals including 7 days after each immunization will not be analyzed.

AEs will be evaluated for the following time interval 'After Day 28 after boost or after prime (if no boost)':

All AEs (regardless of relationship assessment) occurring

- After day 28 after boost immunization
- o If no boost immunization, after 28 days after prime immunization

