#### AEs

The number and percentage of subjects reporting at least one AE and the number of AEs will be summarized for the above defined time interval 'After Day 28 after boost or after prime (if no boost)' and the following AE types:

- Any AE
- Related AE
- Grade >=3 AE

- Related grade >=3 AE
- AEs with dose limiting toxicity (DLT)
- Any serious adverse event (SAE)
- Related SAE
- Deaths
- Any AEs linked to confirmed COVID-19 cases (defined as AEDECOD = 'COVID-19')

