## AE listings

All AEs, AEs with DLT, AEs leading to early discontinuation and SAEs will be listed.

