#### Analysis

The number of subjects with seroconversion will be summarized by number and percentage with 95% confidence interval for all post-baseline time points. The denominator of the percentages will be the number of subjects with data available at the respective visit.

Seroconversion data of the functional antibody titer will be listed.

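### SAP 6.1 excludes data after any outside vaccine, not only a SARS-CoV-2 vaccine, so validly collected late titers and safety events drop out of the summaries

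*SAP*

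**What the plan says.** SAP 6.1 sets one rule for the whole plan: "Data assessed after the vaccination with a non-trial vaccine will be excluded from all statistical analyses". The two clarifications under it concern dates only: same-day data stay in, and a missing day is handled by month end. Vaccine type, cohort and safety data are not mentioned.

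The rule reaches two late safety summaries in SAP 6.4.3. One is the interval "All TEAEs assessed as related through visit 10". The other covers events starting more than 28 days after the last dose: "The number and percentage of subjects reporting at least one AE and the number of AEs will be summarized for the above defined time interval". That table includes serious events, deaths and confirmed COVID-19 cases.

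On denominators, SAP 6.1.1 says "Percentages will be calculated based on the number of subjects in the respective analysis set (N) as denominator if not stated differently" and "The SAF will be used for analysis of safety and adverse events data". Seroconversion differs. SAP 6.5.3 says "The denominator of the percentages will be the number of subjects with data available at the respective visit".

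SAP 6.4.3 also provides listings: "All AEs, AEs with DLT, AEs leading to early discontinuation and SAEs will be listed".

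In the protocol, Section 7.2 withdraws subjects, and Section 8.3.1 ends AE/SAE collection, only in Cohorts 11 to 13 and only after an outside SARS-CoV-2 vaccine. Section 6.5 also names SARS-CoV-2 vaccines only. Its discontinuation sentence carries no cohort limit but refers to Section 7.2. Inclusion criterion 13 bars every vaccine until 28 days after the last trial dose. After that, outside vaccines of any kind are recorded in the CRF.

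**The concern.** The SAP discards data that the protocol keeps collecting. An unrelated vaccine gives no reason to doubt a SARS-CoV-2 neutralizing titer, and no reason to delete a serious event or a death. Yet both would leave the tables.

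The two kinds of data are harmed differently. For titers and seroconversion the number of subjects shrinks, but the percentage is still taken among those with data. For adverse events the denominator stays at the full Safety Set, so a subject whose only late event was removed counts as event-free and the percentage is too low. An event starting more than 28 days after the last dose is treatment-emergent only if the investigator judged it related, so what is lost from the related-TEAE interval is the late events attributed to the trial vaccine.

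The rule is also undocumented as a departure. SAP 1 says "Changes from the protocol are documented in Section 7.1 Appendix 1", and Appendix 1 does not mention it.

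**Working it through.** **The plan's own figures.** No figure is attached to this rule. The only planning figures are the detection probabilities in Protocol Table 10, and they reproduce: for 12 subjects and 15% incidence, 1 − 0.85^12 = 85.8%. The point does not depend on them.

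**1. The rules side by side.**

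| Text | Vaccine | Cohorts | Effect |
|---|---|---|---|
| SAP 6.1 | any outside vaccine | all | later data out of all analyses |
| Protocol 7.2 | SARS-CoV-2 | 11–13 | withdrawn from follow-up |
| Protocol 8.3.1 | SARS-CoV-2 | 11–13 | AE/SAE collection ends that day |
| Protocol Table 8, footnote n | SARS-CoV-2 | 11–13 | no further immune sampling |
| Protocol 6.5 | SARS-CoV-2 | none named; cites 7.2 | discontinued |

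Three cases follow.

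- *SARS-CoV-2 vaccine, Cohorts 11–13.* Collection has already stopped, so the SAP rule removes essentially nothing extra.
- *Unrelated vaccine, any cohort.* No protocol rule stops collection. The SAP rule removes titers and safety events.
- *SARS-CoV-2 vaccine, Cohorts 1–10 and 14.* Under 7.2 and 8.3.1 collection continues to Day 184 (related AEs, SAEs, COVID-19 cases; Table 6 footnote j, Table 7 footnote n, Table 9 footnote i), and the SAP rule removes those events. Under Protocol 6.5 read without 7.2, these subjects have left the trial and little is removed.

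**2. Time exposed (nominal days).** The vaccination ban ends on Day 22 + 28 = Day 50 for prime/boost and Day 1 + 28 = Day 29 for single dose.

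- Prime/boost Cohorts 1–10 and Cohort 14: 184 − 50 = 134 days.
- Single dose: 184 − 29 = 155 days.
- Cohorts 11–13, unrelated vaccine only: 134 days of related AEs, SAEs and infections, then 730 − 184 = 546 days of SAEs and infections only.

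**3. Titer visits exposed after an unrelated vaccine.**

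| Schedule | Post-baseline days | After the ban | Exposed |
|---|---|---|---|
| Prime/boost with Visit 5a | 8, 22, 29, 36, 43, 50, 85, 184 | 85, 184 | 2 of 8 |
| Single dose | 8, 22, 29, 43, 85, 184 | 43, 85, 184 | 3 of 6 |
| Cohort 14 | 8, 15, 22, 29, 50, 184 | 184 | 1 of 6 |
| Cohorts 11–13 | 8, 22, 29, 36, 43, 50, 85, 184, 365, 547, 730 | 85, 184, 365, 547, 730 | 5 of 11 |

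Days up to 184 belong to the secondary endpoints in Protocol 3. Days 365 to 730 enter because SAP 6.5 points to Protocol Table 8.

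**4. Effect on an adverse-event percentage.** With N fixed, removing one subject's only late event lowers the percentage by 100/N points:

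- 12-subject cohort: 100/12 = 8.3
- Cohort 14: 100/20 = 5.0
- Cohorts 11 and 13: 100/30 = 3.3
- Cohort 12: 100/90 = 1.1

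These are per-event sizes. The documents give neither vaccine uptake nor late event rates, so no expected bias can be computed.

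**The case against.** **It is probably a slip.** Elsewhere in the current texts, the non-trial qualifier is attached to SARS-CoV-2 vaccination, and the SAP version history describes the rule at version 7 with that limit. The history is only a hint at intent, not evidence of error. It makes a dropped word likely, but programmers will apply the current sentence. Restoring the word would settle the unrelated-vaccine case, not the conditional one.

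**Protocol 6.5 discontinues everyone who takes an outside SARS-CoV-2 vaccine.** This has weight. For Cohorts 1 to 10, the footnotes to Tables 6 and 7 also allow follow-up participation only in trials that do not study COVID-19 vaccines, although exclusion criterion 15 permits BNT162b2 trials. Against this, 6.5 cites 7.2, and 7.2, 8.3.1 and the Amendment 09 rationale all name Cohorts 11 to 13. A reader might infer that events after a SARS-CoV-2 vaccine in Cohorts 1 to 10 and 14 are certainly lost. The documents support that only conditionally.

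**The late safety tables are SAP additions.** Every AE interval in Protocol 9.4.2 ends by 28 days after the last dose. So the Appendix 1 omission is a weak complaint for adverse events. It stands for titers, because Days 85 and 184 are protocol-planned.

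**Events after another COVID-19 vaccine are confounded.** True, and describing only the period before it is a legitimate choice in an open-label descriptive trial. It does not justify deletion after an influenza vaccine, and flagging preserves the distinction without dropping collected events.

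**Nothing is lost for safety review.** All AEs and SAEs are to be listed and expedited reporting is unaffected. That stands, although SAP 6.1 does not say whether listings are exempt. A listing does not correct a tabulated percentage.

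**Conclusion.** Wrong as written; minor. The unrelated-vaccine case holds on any reading of the protocol. The SARS-CoV-2 case in Cohorts 1 to 10 and 14 holds only if Protocol 7.2 and 8.3.1 take precedence over the unqualified sentence in 6.5. Excluding titers after an outside SARS-CoV-2 vaccine is appropriate.

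Two stronger readings are not supported. First, a reader might infer that the primary safety results are compromised. The ban on other vaccines lasts until 28 days after the last dose, so the 7-day reactogenicity and 28-day TEAE windows are largely protected. Second, a reader might count every subject outside Cohorts 11 to 13 as affected. From Protocol Table 5, 72 + 120 + 290 + 72 + 84 = 638, less 30 + 90 + 30 = 150, leaves 488, or 488/638 = 76.5%. That is only a ceiling on who could fall under the conditional case. It assumes that every cohort runs, although Protocol Table 1 notes that BNT162a1 dosing was deferred, and it says nothing about who received an outside vaccine. That number is not given and may be small.

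**What to change.** - **SAP 6.1:** limit the exclusion to immunogenicity data after an outside SARS-CoV-2 vaccine.
- **SAP 6.4.3:** keep all AEs and SAEs collected under Protocol 8.3.1 in the late summaries. Flag them, or show them in a separate row, when onset follows an outside SARS-CoV-2 vaccine.
- **Late tables:** footnote the number of subjects withdrawn under Protocol 7.2, because they remain in the Safety Set denominator even after this change.
- **SAP Appendix 1:** list the rule.
- **Protocol 6.5:** reconcile the discontinuation sentence with 7.2, for example by naming Cohorts 11 to 13 if that is the intent.

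The cost is a few sentences, one flag or row and one footnote. Outside vaccinations are already in the CRF, so no new data are needed. There are two drawbacks. Some flagged events may be due to the outside vaccine. Follow-up after it would also differ within the pooled BNT162b2 column, stopping in Cohorts 11 to 13 and continuing in the others if 7.2 governs; the footnote should say so.

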- o) For subjects who have given consent, one aliquot of the blood sample drawn for analysis of CMI may be used for HLA typing to allow additional analysis of T-cell receptor repertoire and/or phenotypic characterization of T cells specific to vaccine-encoded antigens.
- p) If HLA typing using the blood sample collected with Lithium Heparin is not conclusive, EDTA-blood will be drawn for HLA testing.
- q) When entering the follow-up phase, i.e., after completing the EoT Visit, subjects are allowed to participate in other clinical trials not investigating COVID-19 vaccines or treatments (including immunosuppressants) except COVID-19 vaccine trials with booster BNT162b2 vaccines (i.e., where they are allowed).
- r) Record any medications that trial subjects receive during the trial in the CRF starting after Visit 0 and until the respective EoT Visit; record any vaccination, including SARS-CoV-2 vaccination, that subjects receive after the EoT Visit until the last FU Visit in the CRF.
- s) Subjects who receive non-trial SARS-CoV-2 vaccinations will be discontinued. Information about these vaccinations may be received outside of a planned visit and can be collected remotely, e.g., by phone.

If the boost dose is not administered or if trial subjects permanently discontinued from IMP administration, subjects will complete all assessments listed in the SoA. Updates introduced by amendment 07 only apply for new consenting subjects after approval of the amendment.

AE = adverse event; CMI = cell-mediated immune testing; CRF = case report form; D or d = day; ECG = electrocardiogram; EDTA = ethylenediamine tetraacetic acid; EoT = end of treatment (Visit); FU = follow-up (visit); h = hour(s); HLA = human leukocyte antigen; Day 0 = one day before Day 1; IMP = investigational medicinal product; min = minute(s); SAE = serious adverse event; SARS-CoV-2 = the virus leading to COVID-19; SoA = Schedule of Activities; WOCBP = women of childbearing potential.

BioNTach SE	Clinical Trial Protocol	Page 30 of 113
BioNTech SE	including Amendments Nos. 01 to 09	Version: 13.0
Confidential	BNT162-01	Date: 12 JAN 2022

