For the immunocompromised cohort (Cohort 13); volunteers who have previously received solid organ transplant, or peripheral blood stem cell transplantation  $\geq$ 6 months after transplantation, or individuals with HIV infection with a CD4+ T-cell count of  $\geq$ 200 x 10^6/L at Visit 0. Individuals with lower T-cell counts will be excluded from the trial on the basis that this represents a significant medical complication. In the clinical judgment of the investigator, volunteers must be immunocompromised but otherwise healthy. After consultation with the Medical Monitor, this may include individuals receiving immunosuppressant therapy due to another confounding disease at least 2 wks prior to enrollment and/or at least 6 wks following immunization with BNT162b2, and/or individuals with immunosuppressive treatment of an autoimmune disease if the disease is stable.

- 6. WOCBP must have a negative beta-human chorionic gonadotropin urine test at Visit 0 and Visit 1. Women that are postmenopausal or permanently sterilized will be considered as not having reproductive potential.
- 7. WOCBP must agree to practice a highly effective form of contraception during the trial, starting after Visit 0 and continuously until 60 d after receiving the last immunization. WOCBP must agree to require their male partners to use condoms during sexual contact (unless male partners are sterilized or infertile).
- 8. WOCBP must confirm that they practiced at least one highly effective form of contraception for the 14 d prior to Visit 0.
- 9. WOCBP must agree not to donate eggs (ova, oocytes) for the purposes of assisted reproduction during trial, starting after Visit 0 and continuously until 60 d after receiving the last immunization.
- 10. Men who are sexually active with a WOCBP and have not had a vasectomy must agree to practice a highly effective form of contraception with their female partner of childbearing potential during the trial, starting after Visit 0 and continuously until 60 d after receiving the last immunization.
- 11. Men must be willing to refrain from sperm donation, starting after Visit 0 and continuously until 60 d after receiving the last immunization.
- 12. They must have confirmation of their health insurance coverage prior to Visit 0.
- 13. They must agree to not be vaccinated during the trial, starting after Visit 0 and continuously until 28 d after receiving the last immunization.

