#### Immunogenicity Set (IMM)

The immunogenicity set is defined as all subjects who received at least one dose of IMP and have at least one post-baseline functional antibody titer immunogenicity assessment.

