#### 6.1.3. Missing Data

As a general rule, missing data will not be substituted (i.e., missing data will not be replaced but will be handled as "missing" in the statistical evaluation), with the following exception for summary analyses:

Clinical safety laboratory variables given as '<xx' will be evaluated as 0.5 \* xx in the summary tables. In the listings they will be displayed as "<xx" or similar.

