## 6.5. Secondary Analyses

Hereinafter, the secondary analyses for Part A are described.

Secondary endpoints are functional antibody responses, fold increase in functional antibody titers and the number of subjects with seroconversion. All secondary analyses will be performed using the IMM and possibly additionally the IMMPP population, see section 5.1.

All secondary analysis endpoints will be summarized by group (i.e. by vaccine type and cohort) and all cohorts combined for each type (cohort-total).

The functional antibody response will be assessed at the time points indicated in the tables 6, 7, 8 and 9 of the protocol.

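### For month-only vaccination dates SAP 6.1 cuts off at month end, so titers drawn after an outside SARS-CoV-2 vaccination could stay in the analysis

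*SAP*

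**What the plan says.** SAP 6.1 gives a general rule: "Data assessed after the vaccination with a non-trial vaccine will be excluded from all statistical analyses". Two clarifications follow. When the date is known, "Data assessed on the same day as the non-trial vaccination will remain in the analysis". When the day is missing but month and year are available, only "data assessed after the last day of the respective month will be excluded from statistical analysis".

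The surrounding provisions are:

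- **Analysis set.** The immunogenicity set (SAP 5.1) requires one dose and that subjects "have at least one post-baseline functional antibody titer immunogenicity assessment". It sets no condition on outside vaccination. The per-protocol repeat is optional (SAP 6.1.1).
- **Missing data.** SAP 6.1.3: "As a general rule, missing data will not be substituted". The one exception there concerns safety laboratory values.
- **Time points.** SAP 6.5: "The functional antibody response will be assessed at the time points indicated in the tables 6, 7, 8 and 9 of the protocol". Those schedules include draws at Day 85 (except Cohort 14) and Day 184, and at Days 365, 547 and 730 for Cohorts 11 to 13.
- **Vaccination restriction.** Protocol 5.1.1, criterion 13: "They must agree to not be vaccinated during the trial, starting after Visit 0 and continuously until 28 d after receiving the last immunization".
- **Sampling stop.** Protocol Table 8, footnote n, ends immunogenicity sampling at follow-up visits for subjects given a non-trial SARS-CoV-2 vaccine. It applies to Cohorts 11 to 13 and came with amendment 09 (Section 10.10.10). On how the site learns of the vaccination, footnote s says: "Information about these vaccinations may be received outside of a planned visit and can be collected remotely, e.g., by phone".
- **Discontinuation.** Protocol 7.2 names Cohorts 11, 12 and 13. Protocol 6.5 discontinues trial subjects given such a vaccine without naming cohorts, and refers to 7.2.

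**The concern.** The partial-date clarification gives a result that its parent rule forbids. A subject vaccinated outside the trial on the 3rd and bled on the 24th of the same month is excluded if the day was recorded and kept if only the month was. Nothing else in the SAP removes or flags the value.

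A non-trial SARS-CoV-2 vaccine can raise the functional titer that forms the secondary endpoint. A retained value would enter the geometric mean titer (GMT), the geometric mean fold rise (GMFR) and the seroconversion count as if the trial vaccine had produced it. If subjects keep to criterion 13, the exposed visits are mainly the follow-up visits, where persistence of response is read (and possibly Day 43 in the single-dose cohorts). In the dose-ranging cohorts, with 12 subjects each, one value has visible weight.

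**Working it through.** The plan states no figure for this rule, so there is none to reproduce. The check has three parts.

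**1. Length of the retained window.** In a month of L days, a vaccination on day v leaves L − v later days inside the cut-off.

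- Maximum, at v = 1: 29 days for L = 30, and 30 days for L = 31.
- Mean over uniform v, (L − 1)/2: 14.5 and 15.0 days.

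**2. Chance that a same-month sample follows the vaccination.** Assume that vaccination day and visit day are independent and uniform within the month. The chance that the visit comes at least d days later is (L − d)(L − d + 1)/(2L²).

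| Lag | L = 30 | L = 31 |
|---|---|---|
| at least 1 day | 29 × 30/1800 = 0.483 | 30 × 31/1922 = 0.484 |
| at least 7 days | 23 × 24/1800 = 0.307 | 24 × 25/1922 = 0.312 |
| at least 14 days | 16 × 17/1800 = 0.151 | 17 × 18/1922 = 0.159 |

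The complement of the first row, about 0.52, is the share of same-month samples taken on or before the vaccination day. Those are valid under SAP 6.1.

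**3. Effect of one affected value.** SAP 6.1.1 computes the GMT by averaging log titers and back-transforming. Multiplying one of n titers by B adds log(B)/n to the mean log, so the GMT is multiplied by B^(1/n). The GMFR changes by the same factor, because the baseline is untouched. The documents do not give B; 4, 10 and 30 are assumed. The n are the planned cohort sizes: 12 (dose-ranging), 20 (Cohort 14), 30 (Cohorts 11 and 13) and 90 (Cohort 12).

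| n | B = 4 | B = 10 | B = 30 |
|---|---|---|---|
| 12 | 1.12 | 1.21 | 1.33 |
| 20 | 1.07 | 1.12 | 1.19 |
| 30 | 1.05 | 1.08 | 1.12 |
| 90 | 1.02 | 1.03 | 1.04 |

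For example, 10^(1/12) = 1.21 and 30^(1/12) = 1.33. If the subject would otherwise have been below a 4-fold increase, the seroconversion rate also rises by 1/n, which is 8.3 percentage points at n = 12.

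With a first-of-month cut-off, the retained window falls to zero and the factor returns to 1.00.

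**The case against.** The strongest reply is that this is an edge case. Harm needs a month-only date, a SARS-CoV-2 vaccine, a scheduled draw between the true date and month end, and time for the titer to rise. No document shows that such a case occurred. That stands: the number is not given and may be zero.

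The protocol also has safeguards. Footnote n stops sampling in Cohorts 11 to 13. Concomitant medication is reviewed at every follow-up visit in all cohorts, and vaccinations after the end-of-treatment visit must be recorded, so the site has an occasion to ask on the day of the draw. Section 6.5 discontinues vaccinated trial subjects in general terms. These points reduce the exposure but do not remove it. Footnote n dates from amendment 09 and covers only three cohorts. Sections 6.5 and 7.2 differ on which cohorts are discontinued. Section 7.2 also asks subjects discontinued after end of treatment to complete the last planned visit, whose schedule includes an immunogenicity draw; that sits uneasily with footnote n.

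Three stronger readings are tempting, and the documents do not support them:

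- A reader might infer that boosted titers are in fact being analysed. The text shows only that they could be.
- A reader might infer that the error is always upward. SAP 6.1 covers any non-trial vaccine, and only a SARS-CoV-2 vaccine would plausibly raise this titer. A sample taken within days of the dose may not yet be raised. The 48% therefore overstates the share of materially raised values.
- A reader might picture late visits with a handful of subjects left, where one value would dominate. No remaining numbers are given. The depletion that the protocol describes concerns Cohorts 11 to 13, which have the sampling stop. The secondary time points listed in protocol Section 3 and SAP 1.1 end at Day 184.

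Finally, the month-end rule may be a deliberate clarification: the SAP version history records one in version 8. It also resembles the SAP's practice, for reactions and adverse events with missing dates, of keeping what cannot be ruled out. For events, keeping is the cautious choice. For titers meant to reflect the trial vaccine alone, the cautious choice is the opposite.

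**Conclusion.** The concern holds in a limited form. As written, the partial-date clarification contradicts the rule it clarifies, and up to 29 or 30 days of post-vaccination titers could be kept for an affected subject. The bias is upward or nil. Where vaccination and visit share a month, the visit follows in about 48% of cases, by at least 7 days in about 31% and by at least 14 days in about 15 to 16%, assuming uniform days and no sampling stop.

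Per affected value, the effect is modest to noticeable in a cohort of 12 and small in a cohort of 90. Its size rests on the assumed fold rise and on full planned cohorts. The analysis is descriptive, the endpoint is secondary, and individual titers are listed. The correction is worth making because it is cheap and restores consistency, not because a distortion has been shown.

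**What to change.** In SAP 6.1, for immunogenicity data and non-trial SARS-CoV-2 vaccines only, replace the partial-date clarification along these lines:

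- Query the site for the day of vaccination before the database snapshot.
- If only month and year remain known, exclude titers from samples taken on or after the first day of that month, unless other information (such as a recorded contact) shows that the sample was taken before, or on the day of, the vaccination.
- Report the present end-of-month rule as a sensitivity analysis.

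Leave the rule for adverse events unchanged. Limiting the change to SARS-CoV-2 vaccines avoids losing titers because of an unrelated vaccine.

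Separately, reconcile protocol Sections 6.5 and 7.2 on which cohorts are discontinued after an outside SARS-CoV-2 vaccination, and reconcile footnote n of Table 8 with the closing assessments in Section 7.2.

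The cost is a short SAP edit, one line of code, some queries and one extra set of summaries. Under the uniform-day assumption about half of the excluded same-month samples would have been valid. The share would be higher where the sampling stop was followed, which is why the query and the exception matter. This should concern few subjects; if there are no month-only dates, no data are lost.
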